10 STUDY MONITORING, AUDITING, AND INSPECTING.....	21
10.1 STUDY MONITORING PLAN	21
10.2 AUDITING AND INSPECTING.....	21
11 ETHICAL CONSIDERATIONS.....	21
12 STUDY FINANCES	21
12.1 FUNDING SOURCE	21
12.2 CONFLICT OF INTEREST.....	21
12.3 SUBJECT STIPENDS OR PAYMENTS.....	23
13 PUBLICATION PLAN	23
14 REFERENCES	23
Appendix A. Data and Safety Monitoring Plan	26

List of Abbreviations

AE	Adverse Event
BOLD	Blood-oxygen-level-dependent
BRIC	Biomedical Research Imaging Center
CHD	Coronary heart disease
COVID-19	Coronavirus Infection
CRF	Case report form
DSMB	Data and Safety Monitoring Board
DVT	Deep vein thrombosis
EC	Ethics Committee
EPDS	Edinburgh Postnatal Depression Scale
EPT	Combined estrogen and progestin treatment (EPT)
FDA	Food and Drug Administration
fMRI	Functional magnetic resonance imaging
FSL	Brain imaging analysis software
HIPAA	Health Insurance Portability and Accountability Act
HRSD	Hamilton Rating Scale for Depression
IDAS	Inventory of Depression and Anxiety Symptoms
IDS	Investigational Drug Service
IRB	Institutional Review Board
IVF	In vitro fertilization
LH	Luteinizing hormone
MASQ-AD	Mood and Anxiety Symptom Questionnaire – Anhedonic Depression Subscale
MATLAB	An interactive environment for numerical computation, visualization, and programming
MID	Monetary Incentive Delay (fMRI task)
MDD	Major Depressive Disorder
PHI	Protected health information
PPD	Postpartum depression
ROI	Region of interest
SAE	Serious Adverse Event
SCID	Structured Clinical Interview for DSM-IV-TR Axis-I Disorders
STRAW	Stages of Reproductive Aging Workshop
TSEC	Tissue Selective Estrogen Complex
UNC-CH	University of North Carolina at Chapel Hill
WHI	Women's Health Initiative

Study Summary

Title	Effects of a Tissue Selective Estrogen Complex on Depression and the Neural Reward System in the Perimenopause							
Short Title	Duavee							
Protocol Number	IRB# 18-2129							
Phase	N/A							
Methodology	Experimental study							
Study Duration	12-24 months							
Study Center(s)	Single-center							
Objectives	
There are two practical objectives:
 
1. To determine the extent to which TSEC reduces anhedonia and other depressive symptoms in PM-MDD. Anhedonia and other depressive symptoms will be assessed at baseline and following 3 weeks of TSEC administration.
 
2. To quantify the effect of TSEC on the neural reward system in PM-MDD. We will use fMRI at baseline and following TSEC treatment in PM-MDD to probe frontostriatal reward circuitry. We also will compare the effects of TSEC and ERT in PM-MDD.
							
Number of Subjects	20							
Diagnosis and Main Inclusion Criteria	
Women with Perimenopausal Depression
 
1) The anchor for the staging system is the last menstrual period (LMP) we will enroll women who have ≥ 2 skipped cycles and an interval of amenorrhea ≥ 60 days, consistent with the late menopause transition (stage -1). Women who meet these criteria will not require an FSH level. Women who have taken oral contraceptives continuously for relief of perimenopausal symptoms and women who have had hysterectomies (with ovaries remaining intact) will be exempt from our LMP criteria, and their perimenopausal status will be determined by FSH level instead (FSH ≥ 14).
 
2) 44-55 years old;
 
3) current diagnosis of MDD with an onset associated with menstrual cycle irregularity. Past mania, psychosis, suicide attempts, and alcohol or drug dependence, as determined by the SCID are exclusionary. All other current comorbid psychiatric illnesses, as determined by the SCID, will be reviewed with our primary investigator (PI) to determine eligibility on a case-by-case basis.
							
Study Product, Dose, Route, Regimen	
Study Product
 
Conjugated estrogens/bazedoxifene (Duavee)
 
Active ingredients: conjugated estrogens, bazedoxifene acetate
 
Chemical name: sodium estrone sulfate and sodium equilin sulfate, and sodium sulfate conjugates, 17α-dihydroequilin, 17α-estradiol, and 17β-dihydroequilin; 1H-Indol-5-ol, 1-[[4-[2-(hexahydro-1H-azepin-1-yl)ethoxy]phenyl]methyl]-2-(4-hydroxyphenyl)-3-methyl-, monoacetate
 
  
 Drug	Dosage	Formulation	
   
 Conjugated estrogens/bazedoxifene	0.45 milligrams/20 milligrams/day	Oral tablet	
  
 
Route:
		Drug	Dosage	Formulation	Conjugated estrogens/bazedoxifene	0.45 milligrams/20 milligrams/day	Oral tablet
Drug	Dosage	Formulation						
Conjugated estrogens/bazedoxifene	0.45 milligrams/20 milligrams/day	Oral tablet						

	Drug	Route of Administration
	Conjugated estrogens/bazedoxifene	Oral
Regimen:		
Once determined eligible and physically well, participants with perimenopausal depression will receive a tissue selective estrogen complex (TSEC) (conjugated estrogens/bazedoxifene, 0.45mg/20mg) for 3 weeks. Prior to beginning medication, women will have a basic lab panel and serum pregnancy test, pelvic exam, breast exam, and PAP smear. Participants who can provide record of a pelvic exam and breast exam within the past year and normal pap results within the past three years will be permitted to decline the GYN exam. Women will be seen in the clinic each week during TSEC administration to assess blood levels of estradiol and mood symptoms.		
Duration of administration	3 weeks	
Reference population	Perimenopausal women, non-depressed	
Statistical Methodology:	We will test our H1 hypothesis using a paired t-test of MASQ Anhedonia scores at visit 1 (pre-treatment) and visit 6 (post-treatment). We will test our H2 hypothesis using a paired t-test to compare activity in 3 regions of interest (ROIs)—caudate, putamen, and nucleus accumbens—at the pretreatment and posttreatment scans.	

1 Introduction

This document is a protocol for a human research study. This study is to be conducted according to US and international standards of Good Clinical Practice (FDA Title 21 part 312 and International Conference on Harmonization guidelines), applicable government regulations and Institutional research policies and procedures.

1.1 Background

Despite decades of clinical research, affective disorders continue to affect 20.9 million Americans each year and remain the leading cause of disability worldwide¹. Unraveling the pathophysiology of affective disorders has been uniquely challenging because depressive syndromes are heterogeneous and have diverse etiologies². Attempts to identify genetic and neural biomarkers that would improve the prediction of susceptibility, course of illness, and treatment response have yielded inconsistent results. One way to solve the problem of etiological diversity and diagnostic heterogeneity is to identify a homogeneous depression subtype with an identified etiology. Reproductive affective disorders (i.e., premenstrual dysphoric disorder, postpartum depression, and perimenopausal depression) represent more homogeneous subtypes, and a clear role for reproductive steroids has been established in these conditions³. Thus, we propose to study the pathophysiology of affective dysfunction by examining neural function in women with a specific depression subtype, perimenopausal depression.

Women with perimenopausal depression represent the ideal population in which to study the neural biomarkers of reproductive affective dysfunction because the presumptive etiology—ovarian hormone withdrawal—is objectively measurable and amenable to manipulation. Evidence supporting the role of ovarian hormone withdrawal in the etiology of perimenopausal depression includes the following: perimenopausal women show a temporal association between ovarian hormone withdrawal and the onset of mood symptoms in the late perimenopause⁴; treatment with estrogen reduces mood symptoms⁵; and blinded estradiol withdrawal re-precipitates depression in women with a history of perimenopausal depression (manuscript in preparation). Thus, perimenopausal depression represents a relatively pure phenotype with respect to the presence of hormone sensitive depression. Focusing on a homogeneous etiology will increase the likelihood of identifying meaningful neurobiological markers⁶.

One of the most powerful tools for understanding the neural mediators of complex behaviors is brain imaging⁷. Although the mechanisms by which reproductive steroids modulate human behavior is relatively unknown, the application of both modern imaging techniques and knowledge of the neurocircuitry underlying fundamental human and animal behaviors should permit us to define more precisely the means by which changes in reproductive steroids elicit depression in some, but not other, individuals.

A fundamental behavior that is dysregulated in depression is reward responsiveness⁸. Reduced responsiveness to rewards contributes to the clinical phenomenon of anhedonia (i.e., loss of interest or pleasure in rewarding activities)⁵, a cardinal feature of depression⁹. In individuals with depression, anhedonia is associated with frontostriatal hypoactivity during reward processing¹⁰. Frontostriatal reward circuit dysregulation may be particularly central to perimenopausal depression. Estradiol modulates reward responsiveness in rodents^{11, 12} and a recent human study demonstrated an association between estradiol levels and frontostriatal reactivity to reward during the menstrual cycle in healthy women¹³. Thus, the frontostriatal reward system is regulated by estradiol and implicated in major depression. However, the effects of estradiol withdrawal and administration on frontostriatal reward circuitry have never been examined directly, and the extent to which frontostriatal dysregulation mediates the effects of estradiol withdrawal on depressive symptoms remains unknown.

While estrogen replacement therapy acts as an antidepressant, many women elect not to take estrogen and many physicians discourage its use because of the risk of long-term negative health effects, including breast and uterine cancer. Estrogens can be paired with selective estrogen receptor modulators (SERMs), synthetic non-steroidal agents that have estrogen agonist and antagonist effects in different tissues, to block the negative effects of estrogen on non-target tissues, including the reproductive organs and cardiovascular system, while allowing estrogen to exert effects on target tissues like the brain [14]. The first such tissue selective estrogen complex (TSEC) approved by the FDA is Duavee, which combines conjugated estrogens and the SERM bazedoxifene [14]. Bazedoxifene has antiestrogenic effects in the endometrium and breast, protecting against uterine and breast cancer, and estrogenic effects in bone, making it a potent preventive agent and treatment for osteoporosis. Duavee has been shown to alleviate hot flashes and vaginal atrophy and prevent osteoarthritis. As a result, Duavee may be an ideal agent to reduce depressive symptoms without the attendant risks of estrogen replacement therapy (ERT) or

adjunctive progesterone treatment. However, the effects of Duavee on depression and the neural reward circuit have never been tested, and one can't infer that estrogen will have the same antidepressant effects in the presence of bazedoxifene (which partially blocks the effects of estrogen in certain tissues). The purpose of our additional treatment arm is to 1) test the antidepressant effects of TSEC, and 2) determine whether TSEC restores neural reward sensitivity, which is blunted in the absence of estrogen.

Thus, we will examine the effects on the neural reward system in perimenopausal women. The proposed experimental study will allow us to answer the following questions: 1) Does the reward system respond to TSEC in those with perimenopausal depression? 2) Does reward system activity at baseline predict the antidepressant effects of TSEC women with perimenopausal depression? Our results will provide critical information about the neuroendocrine pathophysiology of perimenopausal depression and may subsequently contribute to the development of novel pharmacologic interventions.

The proposed study design will allow us to examine the role of frontostriatal hypoactivity in the pathophysiology of perimenopausal depression. It will also allow us to measure frontostriatal responses to TSEC treatment in perimenopausal depression, which has not been previously characterized. This information is critical for understanding the pathophysiology of perimenopausal depression and the mechanisms by which estradiol withdrawal and supplementation have differential effects on mood across women (i.e., why some but not all women become depressed in the perimenopause). These aims are of central relevance to examine the neural pathophysiology of reproductive mood disorders and conduct experimental hormone investigations of the neural circuits contributing to affective illness in women.

The use of ERT to treat perimenopausal major depressive disorder (PM-MDD) is a relatively nascent area of investigation but one of great importance given the large and increasing number of women who enter the perimenopause each year [15, 16] and are potentially at risk for depression [17, 18]. Untreated mood disorders in perimenopausal women contribute significantly to cardiovascular deaths [19]. Perimenopausal women with depressive symptoms seek treatment from gynecologists, psychiatrists, and general practitioners, yet there is neither consensus nor practical guidelines for preventing and treating perimenopausal depression. Moreover, as mentioned above, many women and physicians do not pursue ERT because of the potential adverse consequences and the need for adjunctive treatment with progesterone to protect the endometrium, which can have negative mood consequences in women who are hormone sensitive. Further, traditional antidepressants are not a viable therapeutic option for PM-MDD consequent to limited efficacy [20, 21] and fears regarding side effects and stigma [22, 23]. Because TSEC addresses the main potential problems of ERT, this research will provide important information for 1) developing new medications for PM-MDD, and 2) understanding the neural mechanisms that contribute to depression during periods of reproductive hormone change.

We will be able to determine whether Duavee can be used to treat PM-MDD and the brain circuits involved in depression and its treatment. This research will also provide information essential for 1) identifying which patients will benefit most from hormone therapies and 2) developing new medications for PM-MDD.

We have elected not to include a placebo control condition, as many studies in the field of affective neuroscience forgo placebo controls when examining the effects of drugs on neural circuitry^{14, 15}. If, however, the expense associated with fMRI and sample size were not concerns, the inclusion of a placebo condition would allow us to control for the potential variance associated with repeated fMRI and to examine the potential placebo effects of medication taking on frontostriatal circuitry. Thus, the proposed study will provide pilot data for a larger, randomized, placebo-controlled study with sufficient power to compare treatment and placebo responders and non-responders, which will allow us to further elucidate the precise relationships between changes in frontostriatal activation, TSEC, and changes in mood. Nevertheless, results of the proposed study will provide critical information about the involvement of frontostriatal circuitry in the pathophysiology of perimenopausal depression and the antidepressant effects of TSEC treatment.

1.2 *Investigational Agent.*

CONJUGATED ESTROGENS/BAZDOXIFENE (DUAVEE)

[figure not shown]
Description

DUAVEE (conjugated estrogens/bazedoxifene) tablets contain conjugated estrogens with bazedoxifene, an estrogen agonist/antagonist. Conjugated estrogens are purified from pregnant mares' urine and

consist of the sodium salts of water-soluble estrogen sulfates blended to represent the average composition of material derived from pregnant mares' urine. Conjugated estrogens are a mixture of sodium estrone sulfate and sodium equilin sulfate, and also contain as concomitant components, sodium sulfate conjugates, 17 α -dihydroequilin, 17 α -estradiol, and 17 β -dihydroequilin.

Bazedoxifene is supplied as the acetate salt (bazedoxifene acetate) and has the chemical name 1*H*-Indol-5-ol, 1-[[4-[2-(hexahydro-1*H*-azepin-1-yl) ethoxy]phenyl]methyl]-2-(4 hydroxyphenyl)-3-methyl-, monoacetate. The empirical formula is C₃₀H₃₄N₂O₃ • C₂H₄O₂, and the molecular weight is 530.65.

Bazedoxifene acetate is a white to tan powder. The aqueous solubility of bazedoxifene is pH- dependent. Solubility is higher at lower pH. The solubility of bazedoxifene acetate in unbuffered sterile water was measured to be 923 microgramsA/mL at pH 5.4. The following represents the chemical structure of bazedoxifene acetate:

DUAVEE is available for oral administration as tablets containing 0.45 mg of conjugated estrogens with 20 mg of bazedoxifene (equivalent to 22.6 mg of bazedoxifene acetate). Each tablet of DUAVEE contains the following inactive ingredients: calcium phosphate tribasic, hydroxypropyl cellulose, microcrystalline cellulose, powdered cellulose, hypromellose, lactose monohydrate, magnesium stearate, polyethylene glycol, sucrose, ascorbic acid, sucrose palmitic acid ester, hydroxyethylcellulose, titanium dioxide, red iron oxide, yellow iron oxide, black iron oxide, povidone, polydextrose, maltitol, poloxamer 188, propylene glycol, and isopropyl alcohol.

Pharmacology

DUAVEE pairs conjugated estrogens with bazedoxifene. Conjugated estrogens and bazedoxifene function by binding to and activating estrogen receptors (ER) α and β , which vary in proportion from tissue to tissue. Conjugated estrogens are composed of multiple estrogens and are agonists of ER- α and β . Bazedoxifene is an estrogen agonist/antagonist that acts as an agonist in some estrogen-sensitive tissues and an antagonist in others (e.g., uterus). The pairing of conjugated estrogens with bazedoxifene produces a composite effect that is specific to each target tissue. The bazedoxifene component reduces the risk of endometrial hyperplasia that can occur with the conjugated estrogens component.

Pharmacodynamic studies have not been conducted with DUAVEE.

Summary of Previous Human Experience

We will enroll perimenopausal women to undergo TSEC supplementation using an existing recruitment infrastructure. We currently are assessing the neural reward system in PM-MDD using functional magnetic resonance imaging (fMRI) at baseline and following ERT in our "Effects of Neural Reward System and Depression in the Perimenopause" study (#13-3572). Over the 45 months of

recruitment with ads that specify no current depression, 10,721 women were screened, 244 (2%) of whom were not eligible based on current MDD symptoms.

Support for the hypotheses comes from our lab's own research and that of others, to include:

1. **Estradiol withdrawal precipitates anhedonia in rats, and decreasing estradiol levels are associated with increasing negative mood symptoms in women**¹¹. These results support our ability to conduct successful research in the area of reproductive mood disorders. Our current hypotheses are consistent with this prior research and suggest that the results may have implications for reproductive mood disorders.
2. **Estradiol withdrawal is associated with the onset of perimenopausal MDD, and estradiol treatment reduces perimenopausal MDD symptoms compared with placebo.** In a 5-year longitudinal study of 29 women, a 14-fold increase in MDD was observed in the 24 months surrounding menopause⁴. In a larger cross sectional study (n=116), depressive episodes were significantly more likely during the late perimenopause compared with the pre-, early-, and post-menopause¹⁶. Although estradiol levels are highly variable in regularly cycling women and during the pre- and early perimenopause, the average level of circulating estradiol declines dramatically during the transition from early to late perimenopause²⁰, which is accompanied by an increased incidence in MDD^{4, 16}. Depressive symptoms significantly decreased following 3 weeks of estradiol treatment in 34 women with perimenopausal MDD compared with baseline and women taking placebo⁵ (Figure 1c). Moreover, despite comparable ovarian hormone levels in women with perimenopausal MDD compared with controls^{4, 17}, women with a history of perimenopausal MDD (but not those lacking that history) rapidly experience depression recurrence when blindly withdrawn from estradiol. Thus, estradiol withdrawal appears to trigger perimenopausal MDD in susceptible women, and three weeks of treatment with estradiol is sufficient to treat perimenopausal MDD.
3. **Active MDD symptoms and MDD risk are associated with frontostriatal hypoactivity.** Individuals at high risk for MDD show reduced frontostriatal activation during the proposed monetary incentive delay task, and the degree of activation is associated with the severity of self-reported rumination among those at high risk for MDD¹⁸.
4. **Estradiol levels are associated with increased reward-related neural function during the menstrual cycle in non-depressed women.** Estradiol levels were positively correlated with activation of the dorsolateral and frontopolar cortices¹⁹, which is consistent with our hypothesis that estradiol supplementation will increase activation in frontal regions.
5. **The proposed monetary incentive delay (MID) task induces frontostriatal activation during monetary reward in control women.** At baseline, control women enrolled in our R21 study of the effects of a scaled down hormonal model of pregnancy and parturition on mood and brain function showed increased activity in frontostriatal regions (specifically the nucleus accumbens, caudate, thalamus, dorsolateral prefrontal cortex, and frontopolar cortex) during monetary reward. These areas were selectively responsive to reward and not activated during non-reward, indicating that the task reliably activates the regions of interest associated with reward in previous studies.

Status of Drug in Other Countries

To our knowledge, the proposed drugs have not been withdrawn from investigation or marketing in any other country.

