3.1 General Design

Overview. This is an observational, single-center study using tissue-selective estrogen complex (TSEC) to examine the role of frontostriatal hypoactivity in the pathophysiology of perimenopausal MDD. This study will include 6 study visits that will take place over the course of approximately 6 weeks. Out of those 6 visits, 2 of them will require subjects to come to UNC's campus for their MRI visits at BRIC, while the rest of the appointments will be done virtually through HIPAA compliant Zoom, Webex, or phone when zoom is not available. Five visits will require brief in-person contact for phlebotomy, these very brief points of contact will be performed outside the subject's home when possible (i.e. backyard, back porch, or screened porch). In the context of COVID-19, all participants and staff will complete the appropriate screening as recommended by UNC and BRIC policy prior to any in-person contact. During in person visits participants and the study team will be required to wear masks at all times and maintain 6 feet distance when possible to minimize the possibility of COVID-19 transmission. Perimenopausal MDD women will receive Duavee, a TSEC, for 3 weeks. FMRI sessions will occur at baseline and at the end of the third week of medication administration. The procedures that will take place are outlined in **Table 1** and detailed below.

Table 1. Study Procedures and Timeline

Study Visits	1	2	3	4	5	6
Maximum duration of in-person visit (hours)		1	2	0.15	0.15	2
Consent	X					
OBGYN Exam		X				
fMRI			X			X
PRT			X			X
Venipuncture		X	X	X	X	X
SCID	X					
SNAP	X		X	X	X	X
HAM-D	X		X	X	X	X
IDAS	X		X	X	X	X
GCS	X		X	X	X	X
PSQI			X			X
HHQ						X
THQ						X
Duavee Rx Provided			X	X	X	
Payment	\$100	\$30	\$150	\$35	\$35	\$150

Participants. Participants will include healthy, unmedicated perimenopausal women ages 44-55 with (n=20) current major depression.

Hormone Administration.

Prior to beginning medication, women will have a basic lab panel and serum pregnancy test, pelvic exam, breast exam, and PAP smear. Participants who can provide record of a pelvic exam and breast exam within the past year and normal pap results within the past three years will be permitted to decline the GYN exam. Women will be seen in the clinic each week during medication administration to assess blood levels of estradiol and mood symptoms.

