7.2 Statistical Methods

Aim 1: Determine the extent to which TSEC reduces anhedonia and other depressive symptoms in PM-MDD. Anhedonia and other depressive symptoms will be assessed at baseline and following 3 weeks of TSEC administration. Null hypothesis (H0): TSEC has no salutary effect on depression. Alternative hypothesis (H1): TSEC reduces depression as evidenced by 1) a statistically significant decrease in average MASQ Anhedonia scale score following 3 weeks of treatment, and 2) a clinically significant increase of 1 SD in MASQ Anhedonia scale score. We will test this hypothesis using a paired t-test of MASQ Anhedonia scores at visit 1 (pre-treatment) and visit 6 (post-treatment).

Aim 2 (Exploratory): Quantify the effect of TSEC on the neural reward system in PM-MDD. We will use fMRI at baseline and following TSEC treatment in PM-MDD to probe frontostriatal reward circuitry. We also will compare the effects of TSEC and ERT in PM-MDD. Null hypothesis (H0): TSEC has no meaningful effect on activity of the neural reward circuit in response to rewards. Alternative hypothesis (H1): TSEC reduces increases neural responsiveness to reward in the frontostriatal reward circuitry as evidenced by increased activation of the caudate, putamen, and nucleus accumbens in PM-MDD in response to reward following TSEC administration (compared with baseline). We will test this hypothesis using a paired t-test to compare activity in 3 regions of interest (ROIs)—caudate, putamen, and nucleus accumbens—at the pretreatment and posttreatment scans.

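### Section 1.1 and H1 claim efficacy that a single-arm pre-post test cannot show, and the Aim 1 test counts untreated change before visit 3 as drug effect

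*Combined protocol and SAP*

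**What the plan says.** Section 1.1 (Background) states the purpose in terms of efficacy: "We will be able to determine whether Duavee can be used to treat PM-MDD". Section 7.2 carries this into the Aim 1 hypothesis: "TSEC reduces depression as evidenced by 1) a statistically significant decrease in average MASQ Anhedonia scale score following 3 weeks of treatment". A second criterion follows, a clinically significant change of 1 SD. It is worded as an increase, and the SD is not defined. The only Aim 1 analysis is given as "We will test this hypothesis using a paired t-test of MASQ Anhedonia scores at visit 1 (pre-treatment) and visit 6 (post-treatment". Section 2 and Appendix A repeat the same hypothesis and test.

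Section 1.1 also says "We have elected not to include a placebo control condition", and describes the study in these terms: "Thus, the proposed study will provide pilot data for a larger, randomized, placebo-controlled study". The benefits that it says a placebo arm would bring concern imaging: "the inclusion of a placebo condition would allow us to control for the potential variance associated with repeated fMRI". The only other benefit that it names is again about the brain, namely that the investigators could "examine the potential placebo effects of medication taking on frontostriatal circuitry". Mood is not mentioned there.

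On timing, section 3.1 says "This study will include 6 study visits that will take place over the course of approximately 6 weeks", with 3 weeks on drug. Sections 5.7 and 6 have the whole drug supply handed over at visit 3. Table 1 ticks drug supply at visits 3, 4 and 5, so visit 3 is the earliest on either account. Table 1 schedules HAM-D and IDAS at visits 1, 3, 4, 5 and 6.

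**The concern.** Two things go wrong together.

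First, the stated conclusion is causal, but the comparison has no concurrent control. Women enter with current major depression. Natural course, regression to the mean and expectancy would all tend to lower scores over six weeks, in the same direction as a drug effect.

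Second, the Aim 1 test adds to this without need. Visit 1 is the SCID eligibility visit, and no drug is taken until visit 3. A visit 1 to visit 6 comparison therefore credits TSEC with whatever happened during the untreated lead-in. Pre-dose mood scores at visit 3 are already scheduled, but no analysis uses them. The two aims also start from different points: the pretreatment scan for Aim 2 is at visit 3, whereas the pretreatment score for Aim 1 is at visit 1.

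At stake is how a positive result is read. By the plan's own wording it would be reported as showing that Duavee treats perimenopausal depression, when some or all of the fall could have occurred without it.

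**Working it through.** **Inputs.** From section 7.1: n = 20, power 80%, effect size 0.7. Assumed: two-sided alpha 0.05 (none is stated) and all 20 women analysed (section 7.3 keeps only compliant participants and gives no dropout rate). The documents give no untreated or placebo change on any mood scale, so the size of the non-drug change is also assumed.

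**The plan's own figure.** For a paired t-test the noncentrality is d × √n on n − 1 degrees of freedom. With d = 0.7 this is 0.7 × √20 = 3.13 against a critical value of 2.093, giving power of 84%. The n needed for 80% power is 19, and the effect detectable with 80% power at n = 20 is 0.66. The stated sample size reproduces and is slightly conservative. The same arithmetic applies to a mean change that has nothing to do with the drug.

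**Inert drug, non-drug improvement d₀ (in SDs of the change score), planned test:**

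| d₀ | d₀ × √20 | Probability of significance |
|---|---|---|
| 0 | 0 | 5% |
| 0.2 | 0.89 | 14% |
| 0.3 | 1.34 | 25% |
| 0.4 | 1.79 | 40% |
| 0.5 | 2.24 | 56% |

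**Effect of the second criterion.** Suppose it means a mean fall of at least 1 SD of the score, and the test-retest correlation is r (assumed). The SD of the change is √(2(1 − r)) score SDs. At d₀ = 0.5:

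- r = 0.7: SD of change 0.775, expected fall 0.5 × 0.775 = 0.387, standard error 0.775/√20 = 0.173. A mean fall of 1 lies (1 − 0.387)/0.173 = 3.5 standard errors away, so it is very unlikely.
- r = 0.5: SD of change 1.0, expected fall 0.5, standard error 0.224. A mean fall of 1 lies 2.2 standard errors away, about 1%.

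On that reading, drift of this size would seldom satisfy both parts of H1. If the criterion is meant per woman, this calculation does not apply. Read literally, as an increase in the mean score, it contradicts the first part.

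**Lead-in.** About 6 weeks in total less 3 on drug leaves about 3 untreated weeks. The plan does not fix this length.

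**Would subtracting the lead-in change give a test of efficacy?** Consider (visit 6 − visit 3) − (visit 3 − visit 1). For illustration, assume equal correlations of 0.7 and women selected at visit 1 with scores averaging 1 SD above the mean of their reference population. Regression to the mean is then (1 − 0.7) × 1 = 0.3 SD. All of it falls between visits 1 and 3, and none between visits 3 and 6. The contrast has SD √(6 × 0.3) = 1.342.

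- Inert drug: 0.3/1.342 = 0.22 SD in the direction of harm.
- True effect 0.7: (0.7 × 0.775 − 0.3)/1.342 = 0.18, power about 12%. Without regression it would be 0.40 and 40%.
- True effect 1.15: (1.15 × 0.775 − 0.3)/1.342 = 0.44, power about 46%. Without regression it would be 0.66 and 80%.

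In this model a visit 3 baseline removes the regression, whereas the difference of changes counts it against the drug.

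**The case against.** The strongest reply is that section 1.1 discloses the design. It says that there is no placebo condition and that the study is a pilot for a randomised, placebo-controlled trial. That stands, and the documents do not support a charge that the limitation is hidden. But the disclosure sits next to the claim to determine whether Duavee can be used, and the two do not agree. It also names placebo effects only for frontostriatal circuitry, so it does not cover the Aim 1 mood outcome.

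A reader might infer that H1 would be declared on any significant fall, and so take the 14% to 56% as the rate of false efficacy claims. The documents do not support that: H1 has the further 1 SD criterion. The percentages describe the t-test alone.

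A reader might also infer that regression to the mean of a known size is built in. Entry is by SCID diagnosis, with no minimum MASQ, HRSD or IDAS score, and the documents give neither an untreated change nor a test-retest correlation. The direction is plausible, but the size is not known.

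Finally, section 1.2 cites a benefit of three weeks of estradiol over placebo in 34 women. That makes an effect plausible, but section 1.1 itself says that the same antidepressant effect cannot be inferred when bazedoxifene is present.

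**Conclusion.** The point holds as a matter of wording and of the choice of baseline. A single-arm pre-post comparison cannot determine whether Duavee treats perimenopausal depression, and starting it at visit 1 adds untreated change to the apparent drug effect. With an inert drug and assumed non-drug improvement of 0.2 to 0.5 SD of the change, the planned test is significant in about 14% to 56% of trials (n = 20, two-sided 0.05). The second criterion, once it is defined, would lower the rate at which the whole of H1 is met.

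It is tempting to go further and treat visits 1 to 3 as an own control that rescues the efficacy claim. The documents do not support that. The lead-in speaks to natural course and regression to the mean, but not to expectancy or response to taking tablets. Its length is not fixed, and the difference of the two changes can be biased against the drug. It offers nothing for Aim 2, because scans take place only at visits 3 and 6. Nor does the point require a placebo arm in this pilot. It is a cheap improvement.

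**What to change.** 1. In section 7.2, and where it is repeated in the Study Summary, section 2 and Appendix A, use visit 3 as the baseline for the Aim 1 paired test. State that the visit 3 mood scales are completed before the first tablet.
2. Report the untreated visit 1 to 3 change beside the treated visit 3 to 6 change, each with a 95% CI and the elapsed time, for HAM-D, IDAS and MASQ-AD. Do not use the difference of the two changes as a test of efficacy.
3. Reconcile the MASQ-AD schedule first. The Clinical Assessments text in sections 3.1 and 6 has it given at baseline, both fMRI sessions and the weekly visits, but neither Table 1 nor the Appendix A table has a MASQ row. HAM-D and IDAS can be reported this way regardless.
4. Reword the section 1.1 sentence and H1 to say that depressive symptoms decrease from baseline during TSEC treatment. Correct the direction of the 1 SD criterion and define its SD.
5. State that a positive result supports a controlled trial and does not establish efficacy, because expectancy and placebo response are not controlled.

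Cost: wording and two reported changes, with no added visits or participants once the MASQ-AD schedule is settled. The price is a weaker stated conclusion and possibly a smaller pre-post effect from the visit 3 baseline.
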